**Observational Study Information**

Acronym / Title	PARABO - P ain evaluation in R adium-223 (Xofigo®) treated mCRPC patients with b one metastases – a non-interventional study in nuclear medicine centers
Protocol version identifier	1.0
Date of last version of protocol	12 September 2014
IMPACT study number	17550
Study type	 non-PASS  PASS Joint PASS:  YES  NO
EU PAS register number	To be added after registration
Active substance	Radiopharmaceuticals (V10XX03), Radium-223 dichloride
Medicinal product	Xofigo®
Product reference	EU/1/13/873/001
Procedure number	N/A
Marketing authorization holder(s)	Bayer Pharma AG, D-13342 Berlin, Germany
Research question and objectives	This observational prospective single arm cohort study is designed to assess pain and bone pain related quality of life of metastatic Castration Resistant Prostate Cancer (mCRPC) patients receiving Radium-223 in a real life nuclear medicine practice setting. In addition, overall survival, time to next tumor treatment (TTNT), time to first symptomatic skeletal event (SSE), course of blood counts, and safety will be assessed.
Country(-ies) of study	Germany
Author	[name] Bayer Vital GmbH, Medical Department [name], Germany

Marketing authorization holder

Marketing authorization holder(s)	Bayer Pharma AG 13342 Berlin Germany
MAH contact person	[name] Bayer Vital GmbH, Medical Department [name], Germany

The study will be conducted in compliance with the protocol and any applicable regulatory requirements.

Throughout this document, symbols indicating proprietary names (®, TM) may not be displayed. Hence, the appearance of product names without these symbols does not imply that these names are not protected.

1 Table of contents

Observational Study Information	1
Marketing authorization holder	2
1 Table of contents	3
2 List of abbreviations	6
3 Responsible parties	8
3.1 Sponsor / MAH	8
3.2 Collaborators / Committees	9
4 Abstract	10
5 Amendments	14
6 Milestones	14
7 Introduction: Background and Rationale	14
8 Research questions and objectives	16
8.1 Primary objective	16
8.2 Secondary objective(s)	16
9 Research methods	17
9.1 Study design	17
9.1.1 Primary endpoint(s)	17
9.1.2 Secondary endpoint(s)	18
9.1.3 Strengths of study design	19
9.2 Setting	19
9.2.1 Eligibility	19
9.2.2 Inclusion criterion/criteria	20

EFPIA	European Federation of Pharmaceutical Industries and Associations
EMA	European Medicine Agency
ENCePP	European Network of Centers in Pharmacoepidemiology and Pharmacovigilance
EU	European Union
FACT-BP	Functional Assessment of Cancer Therapy Quality of Life Measurement in patients with bone pain
FDA	Food and Drug Administration
GCP	Good Clinical Practice
GPP	Good Publication Practice
GVP	Good Pharmacovigilance Practice
HEOR	Health Economics and Outcomes Research
HR	Hazard Ratio
ICH	International Conference of Harmonization
IEC	Independent Ethics Committee
INN	International Nonproprietary Name
IRB	Institutional Review Board

LPFV	Last Patient First Visit
MAH	Marketing Authorization Holder
mCRPC	Metastatic Castration-Resistant Prostate Cancer
MedDRA	Medical Dictionary for Regulatory Activities
N/A	Not Applicable
NCI-CTCAE	National Cancer Institute-Common Terminology Criteria for Adverse Events
OS	Overall Survival
PASS	Post-Authorization Safety Study
PSA	Prostate Specific Antigen
QoL	Quality of Life
QPPV	Qualified Person Responsible For Pharmacovigilance
QRP	Quality Review Plan
SAE	Serious Adverse Event
SAP	Statistical Analysis Plan
SOP	Standard Operating Procedure
SSE	Symptomatic Skeletal Event
STROBE	Strengthening the Reporting of Observational Studies in Epidemiology
TEAE	Treatment Emergent Adverse Event
TTNT	Time To Next Treatment
WHO DD	World Health Organization Drug Dictionary

3 Responsible parties

3.2 Collaborators / Committees

Contact details of investigators and other site personnel participating in the study are kept in a study tracking database which is available upon request.

Administrative changes of responsible persons will be documented by updating the respective lists, but do not require formal protocol amendments.

4 Abstract

Acronym / Title	PARABO - P ain evaluation in R adium-223 (Xofigo [®]) treated mCRPC patients with b one metastases – a non-interventional study in nuclear medicine centers
Protocol version identifier	1.0
Date of last version of protocol	12 September 2014
IMPACT study number	17550
Study type	 non-PASS  PASS Joint PASS:  YES  NO
Author	[name] Bayer Vital GmbH, Medical Department [name], Germany
Rationale and background	
Prostate cancer is the most common non-cutaneous malignancy in men in Germany. In advanced prostate cancer, the most common site of metastases is the skeletal system which is involved in more than 90% of the castration-resistant prostate cancer patients.
 
The development of bone metastases is a serious threat to the patients' quality of life and survival, with survival being impacted by the number of metastases. Approximately 50% of patients with bone-metastatic prostate cancer die of prostate cancer within 30 months and 80% within 5 years. Patients with castration resistant prostate cancer usually suffer from very painful bone metastases with severe impact on their quality of life.
 
This study called PARABO is to assess pain and bone pain related quality of life of metastatic Castration Resistant Prostate Cancer (mCRPC) patients receiving Radium-223 in a real life nuclear medicine practice setting. In addition, overall survival, time to next tumor treatment, time to first symptomatic skeletal event, course of blood counts, and safety will be assessed.

Research question and objectives	The primary objective of this study is to evaluate pain response during Radium-223 treatment of mCRPC patients in a real life nuclear medicine practice setting.

	
The secondary objectives in this study are:
 
 • To evaluate the change of pain and bone pain related quality of life over time during treatment phase. • To evaluate pain control rate. • To evaluate pain progression rate • To evaluate time to first pain progression. • To evaluate time to first opioid use. • To evaluate covariates on pain response of mCRPC patients during treatment phase. • To evaluate pain response based on extent of bone metastases at baseline • To evaluate the relation between bone uptake in known lesions and pain palliation (only in patients with bone scan prior to start of treatment and a second scan during or within 6 weeks after the end of Radium-223 treatment). • To evaluate Radium-223 treatment patterns • To evaluate the course of blood counts in patients with different extent of disease and in the whole patient population. • To determine treatments and time to subsequent mCRPC treatment (TTNT). • To determine the time to first symptomatic skeletal event (SSE). • To determine overall survival (OS). • Treatment-emergent adverse events (TEAE) (up to 30 days after last administration of Radium-223).
Study design	This study is a prospective, non-interventional, multi-center, single arm cohort study conducted in nuclear medicine clinics and practices throughout Germany. It is planned to enroll 300 patients with Castration Resistant prostate cancer with bone metastases.
Population	The study population will consist of castration resistant prostate cancer patients with bone metastases treated with Radium-223.
Variables	The investigator collects historic data (demographic and clinical characteristics) from medical records if available, or else by interviewing the patient. Likewise, the investigator collects

	
treatment related data during treatment visits and follow-up visits. The patient questionnaires BPI-SF and FACT-BP will be used for pain and quality of life assessment before each treatment with Radium-223.

Data sources	
Treating physician or designated medical person, Radium- 223 administering physician, medical records, routine measurements (e.g. tumor assessment), other physicians, patient questionnaires.

Study size	
To reach a precision of < 20% for the primary outcome pain response, 300 patients have to be included, based on the following assumptions: 70% of patients will be evaluable for the primary analysis of pain response at a post-baseline assessment and 30% to 70% of patients show a pain response.
 
300 patients is a realistic estimate to be enrolled in a two-year enrollment period, based on current patient numbers and available sites for the treatment. With this sample size and a pain response rate of 65% a precision of < 20 % can be reached assuming subgroups to be at least of 1/2 of this size.

Data analysis	
Statistical analyses will be primarily of explorative and descriptive nature. Whenever reasonable, data will be stratified by subgroups (i.e. age, other baseline characteristics).
 
Patients receiving at least one dose of Radium-223 will be considered valid for safety analysis set.
 
Analyses of pain or QoL will be performed for patients with evaluable patient questionnaires (BPI-SF, FACT-BP, respectively) at baseline and at least one post baseline visit. The incidence proportion will be provided, along with the exact 95% confidence interval. A clinically increase or decrease in opioid use will be taken into account as will be defined in the SAP.
 
The primary analysis of pain response will be summarized in the population of patients with a score >1 (0="no pain") for the baseline measurement of the 'Worst Pain'-item of the BPI-SF.
 
Pain, including subgroups considered as covariates, and quality of life assessments will be summarized descriptively including mean and change from baseline. An analysis of covariance model will be used to assess changes in pain severity.
 
Time to event variables (TTNT, SSE, OS) will be summarized using Kaplan-Meier estimates. Median event times together with the 25th and 75th percentiles and associated 95% confidence intervals will be presented.
 
All therapies documented will be coded using the World Health

	
Organization – Drug Dictionary (WHO-DD). Medical history, any diseases and AEs will be coded using the latest Medical Dictionary for Regulatory Activities (MedDRA) version. Incidence of treatment emergent and drug-related AEs will be presented. Additional subcategories will be based on event intensity and relationship to study drug.
 
It is planned to have one interim analysis 6 months after LPFV. This analysis will use uncleaned data and will primarily focus on pain and QoL assessment. The final analysis will be performed after end of the study which is the date the analytical dataset is completely available.

Milestones	
Start of data collection: 01 December 2014
 
End of recruitment: 30 November 2016
 
End of data collection: 31 May 2019
 
Final report of study results: 28 February 2020

5 Amendments

None

6 Milestones

Table 1 presents planned milestones for the project. These milestones are based on a timely review and approval of the project. Administrative changes to milestones due to delays in study preparation and enrollment do not require amendments to the protocol.

Table 1: Milestones

Milestone	Planned date
Start of data collection	01 December 2014
End of recruitment (LPFV)	30 November 2016
Interim analysis	6 months after LPFV (31 May 2017)
End of data collection	31 May 2019
Database cleaned	31 August 2019
Final report of study results	28 February 2020
Registration in the EU PAS register	expected Q4 2014

7 Introduction: Background and Rationale

Prostate cancer is the most common non-cutaneous malignancy in men in Germany. For 2012, 68,260 new cases are estimated (EU: 359,940) and 12,550 died from the disease (EU: 71,020) [1]. The estimated age-standardized rate for prostate cancer incidence in Germany is 114.1 per 100,000 (EU: 110.8) [1]. Incidence rates increase sharply beyond the age of 50 years. For men aged 50-54 years, the incidence rate is 82 per 100,000 men; ten years later, at age 60-64 years, the rate is more than five times higher at 432 per 100,000, and at 70-74 years the rate is almost nine times higher at 722 per 100,000 [2]. Based on our growing and aging population, it is expected that by the year 2030, the burden of prostate cancer will increase to approximately 89,000 new cases and 17,000 new deaths in Germany (EU: 485,000 and 103,000, respectively) [3].

Prostate cancer is unique amongst solid tumors in that the greatest threat to a patient's survival and quality of life is posed by bone metastases rather than visceral involvement. Indeed, nearly all treatments of the advanced stage are directed toward eradicating or limiting osseous metastases or palliating their side effects [4]. Cellular invasion and migration, cell matrix adhesion or cell-to-cell adhesions, interaction with endothelial cells, regulation of growth factors, and stimulation of osteoclasts and osteoblasts are thought to contribute to development of skeletal metastases [5]. Once prostate cancer becomes metastatic, survival of patients depends on the extent of the disease and the site of metastases. The most common site of metastases for advanced prostate cancer is the skeletal

system which is involved in more than 90% of the castration-resistant prostate cancer (CRPC) patients [6, 7].

Prostate cancer cells are stimulated by androgens, in particular testosterone. Conventional androgen deprivation therapy (ADT) in patients with bone metastases aims to reach castration levels of testosterone (i.e. ≤ 50 ng/mL or 1.7 nmol/L) which can be initially effective controlling the metastases in the bone. However, the majority of patients soon become castration resistant, i.e. progression occurs even at castration levels of testosterone [8]. At this stage, the disease can interchangeably be referred to as either CRPC or the older term hormone-refractory prostate cancer (HRPC) [9]. The commonly accepted term “CRPC” is used throughout this document. Already early stages of CRPC with bone metastases are associated with substantial pain and with rising levels of prostate-specific antigen (PSA) as seen in 35% and 90% of patients, respectively. The extent of PSA control after initial ADT affects prognosis: After 7 months of ADT, patients with PSA < 0.2 ng/ml (undetectable) have a better prognosis than patients with PSA ≥ 4 ng/ml [10].

In normal bone tissue, homeostasis is carried out by the balanced interplay between osteoclasts and osteoblasts which are cell types specialized in bone decomposition and bone formation, respectively. In the presence of malignant neoplasms and following hematological dissemination of tumor cells into the bone, bone metastases develop as a result of a pathologic interaction between tumor cells on the one hand and osteoblasts as well as osteoclasts on the other hand.

The development of bone metastases is a serious threat to the patients’ quality of life and survival, with survival being impacted by the number of metastases. Approximately 50% of patients with bone-metastatic prostate cancer die of prostate cancer within 30 months, and 80% within 5 years [11]. The associated complications present a substantial disease and economic burden [12]. Untreated patients face severe morbidity, including bone pain, bone fractures, compression of the spinal cord and hematological consequences of bone marrow involvement such as anemia. As presence of bone metastases represents a major clinical problem for patients with metastatic castration-resistant prostate cancer (mCRPC), specific treatment options for this condition are needed. Control of bone metastases is expected to lead to improved symptoms and quality of life as well as prolonged overall survival.

Radium-223 selectively targets bone metastases with high-energy, short-range alpha-particles. A phase III, double-blind, randomized trial, ALSYMPCA (**Al**pharadin in **S**ymptomatic **P**rostate **C**ancer), was started in 2008 [13]. A total of 921 patients with CRPC and symptomatic bone metastases who were receiving best standard of care and were post-docetaxel or unfit for or declined docetaxel were randomized (2:1) to receive 6 injections of Radium-223 dichloride (50 kBq/kg intravenous) or matching placebo every 4 weeks. The primary endpoint was overall survival. Main secondary efficacy endpoints were time to first skeletal-related event and various biochemical end points. Based on data of an interim analysis (n=809), the study was unblinded in July 2011, since Radium-223 significantly improved OS, compared to placebo (the median OS was 14.0 vs. 11.2 months, respectively; HR=0.70; p=0.002). The updated analysis (performed in June 2012; n=921) also showed that Radium-223 significantly improved OS compared to placebo (median OS 14.9 vs. 11.3 months, respectively; HR=0.70; p<0.001). Symptomatic skeletal events (SSE) were lower in the Radium-223 arm, and time to first SSE was significantly delayed (the median time to SSE was 15.6 months, versus 9.8 months, respectively; HR= 0.66; p<0.001). A low incidence of myelosuppression was observed, with grade 3/4 events of neutropenia (3%) and thrombocytopenia (6%). Adverse events of any grade were described in 93% of the subjects who received radium-223 dichloride; versus 96% in the placebo arm (grade 3/4

adverse events were described for 56% and 62%, respectively). Radium-223 dichloride was authorized in the European Union as Xofigo[®] in November 2013.

Sub-analysis from ALSYMPCA revealed in addition to the improvement in overall survival a pronounced potential for pain reduction, prolonged time to use of external beam radiation therapy (EBRT) for pain palliation and time to opioid use [14]. The distinct reduction of local symptoms from bone metastases delayed substantially the distortion of quality of life (QoL) compared with placebo [15]. This pronounced reduction in tumor related symptoms is an important benefit for patients in the castration resistant stage of prostate cancer where cure is not an option anymore but good symptom palliation the main focus of any treatment.

The effect of Radium-223 on pain and QoL preservation in mCRPC patients was, as described, to some extent demonstrated in the pivotal Phase 3 ALSYMPCA trial. However, this trial was conducted in a closely defined patient population according to strict inclusion and exclusion criteria. This non-interventional prospective study is to further examine the effect of Radium-223 on pain palliation and bone pain related QoL in mCRPC patients in more detail and in a more heterogeneous patient population under routine daily practice conditions in Germany.

To assess pain, the “Brief pain inventory short form” (BPI-SF) will be used. BPI-SF is a short, self-administered questionnaire with 11 items, which was designed to evaluate the intensity of, and the impairment caused by pain. All BPI-SF items are scored using rating scales. Four items measure pain intensity (pain now, average pain, worst pain, and least pain) using 0 (“no pain”) to 10 (“pain as bad you can imagine”) numeric rating scales, and 7 items measure the level of interference with function caused by pain (general activity, mood, walking ability, normal work, relations with other people, sleep and enjoyment of life) using 0 (no interference) to 10 (complete interference) rating scales [16].

For QoL assessment, the questionnaire “Functional Assessment of Cancer Therapy Quality of Life Measurement in patients with bone pain” (FACT-BP) will be used. The FACT-BP consists of 16 items including general functioning and physical and bone pain and uses a 0-4 Likert-scale; recall period of the questionnaire is 7 days.

8 Research questions and objectives

This observational prospective single arm cohort study is designed to assess pain and bone pain related quality of life of metastatic Castration Resistant Prostate Cancer (mCRPC) patients receiving Radium-223 in a real life nuclear medicine practice setting in Germany. In addition, overall survival, time to next tumor treatment (TTNT), time to first symptomatic skeletal event (SSE), course of blood counts, and safety will be assessed.

8.1 Primary objective

The primary objective of this study is to evaluate pain response during Radium-223 treatment of mCRPC patients in a real life nuclear medicine practice setting.

8.2 Secondary objective(s)

The secondary objectives in this study are:

- To evaluate the change of pain and bone pain related quality of life over time during treatment phase.

- To evaluate pain control rate.
- To evaluate pain progression rate
- To evaluate time to first pain progression.
- To evaluate time to first opioid use.
- To evaluate covariates on pain response of mCRPC patients during treatment phase.
- To evaluate pain response related to the extent of bone metastases at baseline
- To evaluate the relation between bone uptake in known lesions and pain palliation (only in patients with bone scan prior to start of treatment and a second scan during or within 6 weeks after end of Radium-223 treatment).
- To evaluate Radium-223 treatment patterns
- To evaluate the course of blood counts in patients with different extent of disease and in the whole patient population.
- To determine treatments and time to subsequent mCRPC treatment (TTNT).
- To determine the time to first symptomatic skeletal event (SSE).
- To determine overall survival (OS).
- Treatment-emergent adverse events (TEAE) (up to 30 days after last administration of Radium-223).

9 Research methods

9.1 Study design

This study is a prospective, non-interventional, multi-center, single arm cohort study conducted in nuclear medicine clinics and practices throughout Germany. Sites are selected based on the experience of the attending physician with the indication and the treatment with Radium-223. It is planned to enroll 300 patients with CRPC with bone metastases for whom the attending physician decided according to his/her medical practice to treat the patient with Radium-223. Treatment with Radium-223 should follow the approved product information.

For each patient, the investigator will document data in standardized case report forms at initial, follow-up and final visits during treatment phase. Data will be collected using electronic case report forms (eCRF). The observation period for each patient enrolled in this study is the time from start of therapy with Radium-223 to death, withdrawal of consent, loss to follow-up or end of this study (maximum of 2 years after last administration of Radium-223), whichever comes first in time.

The medication is used within the routine clinical practice setting. Commercially available product will be used to treat the patients.

9.1.1 Primary endpoint(s)

The primary endpoints are:

- **Pain response** as determined by the worst pain item on the BPI-SF patient questionnaire. A clinically meaningful pain response is defined as an improvement of two points from the baseline BPI-SF worst pain score [17] at any post-baseline assessment.

9.1.2 Secondary endpoint(s)

The secondary endpoints are:

- **Changes of pain over time** by evaluating the worst pain item as well as the subscale scores for pain severity and pain interference as determined by patient responses on the BPI-SF questionnaire. The worst pain item and subscales will be presented separately for each post-baseline assessment.
- **Changes in bone pain related quality of life** as determined by patient responses on the bone pain specific FACT-BP questionnaire. The FACT-BP score will be presented separately for each post-baseline assessment.
- **Pain control rate** as determined by the worst pain item on the BPI-SF patient questionnaire. Pain control is defined as no increase by two points from the baseline BPI-SF worst pain score.
- **Pain progression rate** as determined by the worst pain item on the BPI-SF patient questionnaire. Pain progression is defined as an increase by two points from the baseline BPI-SF worst pain score at any post baseline assessment.
- **Time to first pain progression** is defined as the time between the first injection of Radium-223 until an increase in the BPI-SF worst pain item by at least two points.
- **Time to first opioid use** in patients who did not take opioids at study entry is defined as the time from first injection of Radium-223 until first intake of opioid analgesics.
- **Evaluation of covariates on pain response** of mCRPC patients during treatment with Radium-223. The following covariates will be analyzed:
 - opioid use
 - assessment of extent of bone metastases (<6, 6-20, > 20, superscan)
 - location of bone metastases
 - level of alkaline phosphatase at baseline (<150 mU/l, 150-300 mU/l, and >300 mU/l)
 - PSA level at baseline (<50 µg/l, 50-200 µg/l, and >200 µg/l)
 - WHO pain score at baseline (WHO-Score 0+1 and WHO-Score 2+3)
 - pretreatment with chemotherapy (yes/no)
 - pretreatment with deep androgen ablation by treatment with abiraterone or enzalutamide (yes/no)
 - extent of bone uptake in known lesions (only faint, higher uptake, and strong uptake compared to surrounding bone)

- **Relation between bone uptake in known lesions and pain palliation** (only in patients with bone scan prior to start of treatment and a second scan during or within 6 weeks after end of Radium-223 treatment)
- For **Radium-223 treatment patterns** dosage and number of injections of Radium-223 will be analyzed.
- **Course of blood counts** in patients with different extent of disease and in the whole patient population will be presented as percentage of patients below limit for further injections according to the local product information
- **Treatment-emergent Adverse Events (TEAE)** - Patients will be monitored for TEAE using the NCI-CTCAE Version 4.03. Detailed information collected for each TEAE will include: a description of the event, duration, whether the TEAE was serious, intensity, relationship to Radium-223, action taken, clinical outcome.
- **Time to next tumor treatment(s) (TTNT)** is defined as the time from the first application of Radium-223 until start of next mCRPC treatment including e.g. chemotherapy and/or hormonal treatment.
- **Time to first symptomatic skeletal event (SSE)** is defined as the time between the first injection of Radium-223 until the occurrence of first SSE defined as the first use of external beam radiation therapy to relieve skeletal symptoms, new symptomatic pathological vertebral or non-vertebral bone fractures, spinal cord compression, or tumor-related orthopedic surgical intervention
- **Overall survival** is defined as the time interval from the start of Radium-223 therapy to death, due to any cause. Patients alive at the end of the study will be censored at the last date known to be alive. Date and cause of death will be collected.

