9.3 Variables

The investigator collects historic data (demographic and clinical characteristics) from medical records if available, or else by interviewing the patient. Likewise, the investigator collects treatment related data during treatment visits and follow-up visits. The investigator documents the study-relevant data for each patient in the case report form (CRF). The CRF is available upon request (see Table 4: List of stand-alone documents, Annex 1)

Table 2: Tabulated overview on variables collected during the study

Variables	Baseline and first treatment	Further Treatment visits	Follow-up after end of treatment	Long-term follow-up	End of observation
Date of visit	X	X	X	X	X
Patient informed consent	X				
Demography	X				
Vital Signs	X				
Co-morbidities (medical history, concomitant diseases)	X				
Prostate cancer history (initial diagnosis, diagnostic and therapeutic procedures)	X				
WHO pain score	X	X	X		
Performance Status (ECOG)	X	X	X		
Questionnaires BPI-SF and FACT-BP	X	X	X		
Location of bone pain	X	X	X		
Number and location of skeletal lesions (bone scan)*	X	X	X		
Exposure/treatment (dose of Radium-223)	X	X			
Concurrent diagnostic and therapeutic procedures for mCRPC	X	X			
Laboratory parameters including ALP, PSA, blood counts	X	X	X		
Opioid use	X	X	X	X***	
Concomitant medication	X	X			
Adverse Events	X	X	X**		
Symptomatic skeletal events		X	X	X	
Further treatment for mCRPC		X	X	X	
Survival assessment				X	
Reason for end of observation					X

*If available, an additional bone scan together with an assessment of bone uptake of Radium-223 can be documented independently from visits.

**Up to 30 days after last treatment with Radium-223.

***Only opioid use yes/no and date of first use

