- The course of blood counts will be analyzed. Incidence of blood counts below limit for further injections according to the local product information in patients with different extent of disease

and in the whole patient population will be calculated. The incidence proportion will be provided, along with the exact 95% confidence interval.

- Time to event variables (TTNT, SSE, OS) will be summarized using Kaplan-Meier estimates. Median event times together with the 25th and 75th percentiles and associated 95% confidence intervals will be presented. Censoring rules will be defined in the SAP.
- Incidence of treatment emergent and drug-related AEs will be presented using the NCI-CTCAE Version 4.03. Additional subcategories will be based on event intensity and relationship to study drug.

Further details will be given in the SAP.

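### The blood-count endpoint is fixed as the share of patients below the re-injection limit, which shows no course and does not separate low baseline counts from falls on treatment

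*Protocol*

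**What the plan says.** Section 8.2 sets as an objective the course of blood counts, both by extent of disease and in all patients. Section 9.1.2 turns this into an endpoint by stating that the course "in patients with different extent of disease and in the whole patient population will be presented as percentage of patients below limit for further injections", with the limit taken from the local product information.

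Section 9.7.5 opens with "The course of blood counts will be analyzed" and then names one statistic: "Incidence of blood counts below limit for further injections according to the local product information in patients with different extent of disease", and likewise for the whole population. On that statistic it adds: "The incidence proportion will be provided, along with the exact 95% confidence interval". Neither section mentions the baseline count, change from baseline, values by visit or a shift in grade.

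For pain and for FACT-BP, by contrast, Section 9.7.5 asks for means and change from baseline at each assessment. Table 2 in Section 9.3 schedules blood counts at baseline, at further treatment visits and at the follow-up after treatment. The background in Section 7 lists, among the effects of untreated bone metastases, "hematological consequences of bone marrow involvement such as anemia".

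**The concern.** The named summary does not match the objective. A proportion below a cut-off says how many patients were low. It does not say where counts started, how far they fell, when, or whether they recovered.

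The two sections also leave open who counts as a case. Section 9.7.5 speaks of incidence, which suggests new cases. Section 9.1.2 speaks of the percentage below the limit, which would include a patient who was below it before the first injection. Neither says how such a patient is handled.

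This matters because the percentages are to be shown by extent of disease, and the protocol names a route by which bone disease itself can lower counts. Patients with more extensive disease may start nearer the limit. A higher percentage in that group could then come from a lower start, a larger fall, or both, and the table would not show which. A larger fall in patients who started high could also go unseen because they stay above the limit.

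**Working it through.** The protocol states no figure for this endpoint. Table 3 concerns the primary pain response and does not bear on it. The check is therefore a comparison of the sections, followed by an illustration on assumed values.

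**Does any section supply the missing baseline reference?**
- Section 9.1.2 gives a percentage below the limit, with no baseline reference.
- Section 9.7.5 gives the same quantity as an incidence with an exact interval, with no baseline reference.
- Section 9.7.8 says in general terms that outcomes and safety data will be analysed by baseline factors. It does not name the baseline count.
- Sections 9.1.2 and 9.7.5 also provide treatment-emergent adverse events graded by CTCAE 4.03. Section 11.1 brings a laboratory finding in only when it is judged clinically relevant, and Section 9.7.5 specifies no adverse-event summary by extent of disease.

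**Illustration A: how far a lower start alone can move the percentage.**
- From the protocol: grade 3/4 neutropenia of 3% and thrombocytopenia of 6% in the phase III trial (Section 7). They stand in for the share below the limit, because the limit is not in the document.
- Assumed: counts normal on a suitable scale with SD 1; the same fall in both groups; the less extensive group at the stand-in rate p0; the other group's baseline g SD nearer the limit.
- Formula: share below the limit = Φ(Φ⁻¹(p0) + g).
- For p0 = 6%, Φ⁻¹ = −1.555. With g = 0.5: Φ(−1.055) = 14.6%.
- For p0 = 3%, Φ⁻¹ = −1.881. With g = 0.5: Φ(−1.381) = 8.4%.

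| Baseline gap g | From 3% | From 6% |
|---|---|---|
| 0.25 SD | 5.1% | 9.6% |
| 0.50 SD | 8.4% | 14.6% |
| 0.75 SD | 12.9% | 21.0% |

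**Illustration B: the same point with the fall made explicit.**
- Assumed: baseline mean k SD above the limit, with k = 2.5 for limited and 1.5 for extensive disease; every patient falls by d SD.
- Formula: share below the limit = Φ(−(k − d)).
- No fall (d = 0): Φ(−2.5) = 0.6% and Φ(−1.5) = 6.7%, a gap of 6.1 points.
- Fall of 0.5 SD in both: Φ(−2.0) = 2.3% and Φ(−1.0) = 15.9%, a gap of 13.6 points.
- Mean change from baseline is −0.5 SD in both groups, a difference of 0. That follows directly from assuming an equal fall.
- With k = 2.0 to 1.0 in extensive disease and d = 0 to 1, the gap runs from 1.7 to 43.3 points.

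**Is it enough to remove patients already low at baseline?** Take B with d = 0.5. New cases in limited disease are 2.3 − 0.6 = 1.7 points among the 99.4% at or above the limit at baseline, about 2%. In extensive disease they are 15.9 − 6.7 = 9.2 points among 93.3%, about 10%. The separation makes the proportion interpretable as an incidence, but starting level still drives it. Change from baseline is needed as well.

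**The case against.** It can fairly be said that the share below the re-injection limit is a useful descriptive quantity in its own right. It tells a clinic how often counts reach the level that bears on continuing treatment, and for that purpose the starting value and the cause of a low count do not bias it. Section 9.7.1 calls the analyses primarily explorative and descriptive, and no test between extent groups is planned. This stands, and it is why the percentage should be kept.

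A reader might infer that the protocol will report disease-related cytopenia as a toxicity difference, or that its main marrow-toxicity result is biased. The document supports neither. It nowhere attributes the contrast by extent of disease to Radium-223, and marrow toxicity is also captured through CTCAE-graded adverse events with a recorded relationship to treatment. That route is only partial, for the reasons given in the check.

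A further objection is that change-from-baseline and shift tables are ordinary SAP content, that Section 9.7.5 defers details to the SAP, and that nothing excludes such tables. So it cannot be said that the course will never be shown. But Section 9.1.2 is not silent: it states how the endpoint will be presented, and an SAP that follows it would inherit the mismatch with the objective.

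Two more points stand. The documentary support for lower starting counts is one clause on anemia in a sentence about untreated patients, while the illustration borrows neutropenia and thrombocytopenia rates. And in a single-arm study, advancing marrow disease can also lower counts over time, so change from baseline does not isolate the drug either.

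**Conclusion.** The point holds in a limited form. The protocol fixes a summary for the course of blood counts that shows no course and does not distinguish counts already low at baseline from counts that became low on treatment. Shown by extent of disease, the percentages may reflect starting level as well as decline on treatment, and they should not be read as a difference in marrow toxicity.

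The size is unknown. The figure of 6% becoming 14.6% for a 0.5 SD baseline gap rests on normality, SD 1, an equal fall, an assumed gap and a stand-in for the limit. It shows that the mechanism can matter, not that it will. This is a cheap improvement to one descriptive secondary endpoint and does not touch the primary analysis.

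**What to change.** In Sections 9.1.2 and 9.7.5:
- Keep the percentage below the limit. Report separately the patients already below it at baseline, and count as incident only those at or above it at baseline.
- For each cell line, add values and change from baseline at each injection visit and at follow-up, with the number of patients contributing.
- Add a shift table from baseline to worst on-treatment CTCAE 4.03 grade, derived from the recorded values.
- Give each of these overall and by extent of disease, and state which extent categories apply. Section 9.1.2 defines four, but for the pain covariates.
- State that in a single-arm study even change from baseline cannot fully separate disease progression from drug effect.

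The cost is a few more descriptive tables. No visit, sample or treatment rule changes. Visits follow routine practice and the follow-up visit takes place only where it is routine, so numbers will vary by time point; showing the denominators deals with that.
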